# 8.1 SAMPLE SIZE

Up to 1500 patients with erectile dysfunction (ED) electing to receive a BSC penile prosthesis implant will be included in this registry over a 1- to 2-year enrollment period. A total of more than 500 patients are anticipated to be implanted and entered into the registry database per year of enrollment, based on the following BSC historical estimates of the number of each BSC penile prosthesis type implanted, and assuming 10 to 15 participating physicians:

- 500 AMS 700®
- 15 AMS Ambicor®
- 20 Spectra™

The minimum sample size for multi-center data analysis will depend on the total number of patients, or the number of patients with each type of penile prosthesis implanted for whom sufficient follow-up data on multiple endpoints of interest are available. Generally, a minimum follow-up of at least one year after implantation is desired for analysis of data for the device subsets with previous clinical outcomes reported in the literature (e.g., AMS 700®, AMS Ambicor®). Because clinical data has been published from multiple studies including more than 100 patients implanted with AMS 700® devices in the past decade (since the introduction of the InhibiZone antibioticimpregnated devices and the current MS Pump), analysis of less than 100 patients implanted with these devices with at least one1 year of follow-up is not planned. However, an analysis sample size as small as 10 to 25 patients implanted with the newer Spectra™ or AMS 700® Series devices with the Conceal Low Profile reservoir, with 6 to 12 months of post-implant follow-up, may be of value for publication in the scientific literature due to the lack of any prospective clinical outcomes published to date for these products.

### 8.2 SAFETY OBJECTIVES

Safety will be assessed by collection and review of all reported intra-operative and postoperative device or surgery related clinical study events recorded during the implantation or any follow-up visits (for BSC products only).

#### Endpoint:

- Complications (adverse device effects/events)
  - Intra-operative device or surgery related complications reported during Implantation visit (e.g., cylinder crossover)

- Post-operative device or surgery related complications reported during follow-up (e.g., mechanical malfunction, infection)
- Unanticipated and serious adverse device effects (per ISO 14155:2011)
- Deaths (related to the device or implantation procedure)
- Device Malfunctions
  - Device deficiencies or malfunctions (per ISO 14155:2011)
- Revision procedures related to the device or implantation procedure

#### Statistical Analysis:

Descriptive statistics (number of events, number and proportion of patients) will be summarized by complication category by device type and for the full group. Kaplan-Meier method will be used to estimate the major complication event rate at 1 year postoperative follow up by device type and overall for all BSC penile prostheses recipients.

Descriptions will also be prepared of the following details associated with device related complications in each category, and will include the following as available for each:

- Treatment for complication
- Location of treatment
- Resolution (resolved or continuing)

Additional analyses may be prepared for other follow-up time such as 6 month, 2, 3, 4, and 5 years.

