#### *Recommended for all patients with post-prostatectomy ED or incontinence:*

- AUA-SI/IPSS urinary symptom questionnaire
- UCLA-PCI urinary, sexual and bowel function and bother questionnaire

Any reported intra-operative or post-operative device or surgery related complications will be recorded throughout study follow-up (for BSC products only). This information will include:

- Complication
- Treatment
- Location of treatment

• Resolution (Resolved or Continuing) Potential device or surgery related complications are described in the device specific IFU and OR manuals.

Up to 1500 patients with erectile dysfunction (ED) electing to receive a BSC penile prosthesis implant will be included in this registry.

Analyses of multi-center data for initial publication(s) may be performed after approximately 500 patients complete 1 year follow-up. Additional individual and multi-center data analyses may be performed as warranted throughout the study for publication(s). Analysis for multi-center publication(s) is planned after the study enrollment is complete and all the enrolled patients have completed their one-year and five-year follow-up evaluations, consistent with each physician's standard of care.

Continuous variables will be presented as mean +/- SD; ordinal variables will be summarized using median with interquartile ranges; categorical variables will be presented as count and proportion.

Kaplan-Meier method will be used to estimate the event rate over time by device type for major complications.

For within-patient change at 1 year follow up compared to the baseline visit, signed rank test or paired t-test may be used for continuous variables and McNemar's test may be used for binary variables when applicable. Mixed effects model or Generalized Estimating Equation model may be used to estimate the change from baseline across follow up

Safety/Device Malfunction Assessments:

Statistical Analyses, Including Determination of Sample Size: visits when appropriate.

The data to be collected in electronic data forms will include the following:

Table 1: Electronic	; data	collection	schedule
---------------------	--------	------------	----------

Data	Baseline/ Procedure	Interim Follow-Up*	1 Year Follow-Up*	2 - 5 Year (Annual) Follow-Up*
Date of Informed Consent/first data record	R			
Demographics and Characteristics	R			
ED History	R			
Depression History	0	N/A	0	0
Implantation Procedure Details	R			
Device Use and Satisfaction	N/A	0	R	SE

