# 7.4.1 CLINICAL STUDY EVENTS

Clinical study events to be collected for assessment of safety include complications (adverse device effects/events), device malfunctions, and revision procedures related to the device or implantation procedure. At follow-up, including the required 1-year post-operative visit or telephone call, the following standardized, non-validated question will be used to determine whether any complications with the device have occurred:

• Have you had any surgery on your penis or problems with the device since your penile prosthesis was implanted? (Y/N)

A clinical study event data form will be provided to record any events that occur during or after surgical implantation of a BSC penile prosthesis device. Any reported intraoperative or post-operative device or surgery related complications should be recorded at the time of procedure and any follow-up visits (for BSC products only). The information recorded will include the following:

- Complication
- Treatment
- Location of treatment
- Resolution (Resolved or Continuing)

BSC personnel will follow up with the physician to obtain additional available details, if needed, related to any reported complication that results in a serious adverse device effect, or device deficiency that could have led to a serious adverse device effect, or is severe and may pose unreasonable risk, or potential for death, or serious injury to the patient.

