#### Determination of Patients for Analysis:

All enrolled patients that received a BSC penile prosthesis with data available will be included.

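### Durability is a main objective, but no time-to-event analysis of device malfunction or revision is firmly committed beyond an undefined major-complication curve, although follow-up after year 1 will be unequal

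*Combined protocol and SAP*

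**What the plan says.** Section 3.1 puts durability beside safety, satisfaction and effectiveness in the main objective. Section 2.2 treats five years as the shortest period that counts as long-term follow-up, and section 8 plans an analysis after the 5-year evaluations.

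The endpoint list in section 8.2 has separate entries for device malfunctions and for "Revision procedures related to the device or implantation procedure". It also has an entry for "Post-operative device or surgery related complications reported during follow-up (e.g., mechanical malfunction, infection", so a malfunction can count as a complication too.

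The analysis text of section 8.2 makes two firm commitments. The first is a descriptive summary: "Descriptive statistics (number of events, number and proportion of patients) will be summarized by complication category by device type and for the full group". The second is a time-to-event estimate, planned for the whole cohort as well as for each device: "Kaplan-Meier method will be used to estimate the major complication event rate at 1 year postoperative follow up by device type".

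Later time points are optional: "Additional analyses may be prepared for other follow-up time such as 6 month, 2, 3, 4, and 5 years". The analysis set is: "All enrolled patients that received a BSC penile prosthesis with data available will be included".

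The synopsis describes the curve differently: "Kaplan-Meier method will be used to estimate the event rate over time by device type for major complications". Neither place says which complications are major.

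On follow-up, the synopsis and section 4 require a 1-year evaluation and strongly encourage one at 2 years; the rest follow each physician's practice, up to 5 years. Table 1 requires clinical events to be recorded, where applicable, at every contact. Section 7.4 says physicians should be in touch with patients at least yearly.

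**The concern.** The plan names durability as something to be learned but does not say how it will be estimated. Read literally, the only firm multi-year output for malfunctions and revisions is a count and a proportion by complication category. Even that assumes they are complication categories.

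Some men will be followed for one year and others for five. The analysis set gives no denominator or censoring rule. A crude proportion over such data mixes the failure rate with the length of follow-up. It reads low if every implanted man is counted. It reads high if a man without an event is counted only once he reaches year 5. Device types whose surgeons follow patients for different lengths of time cannot be compared on it.

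The stakes are real for a registry of this kind. Section 4 describes it as an active surveillance system for malfunctions, and section 16 says its safety or performance data may go to regulators.

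**Working it through.** **No plan figure to reproduce.** The documents give no failure rate, retention figure, precision target or durability sample size. The rates below are assumptions that show direction and rough size.

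**Inputs.** Assumed hazard h = 0.02 per year, and assumed share of men followed through years 1 to 5, unrelated to failure: pattern A = 100/90/80/70/60%, pattern B = 100/60/45/35/25%. From section 8.1: 500 AMS 700, 15 Ambicor and 20 Spectra implants a year for 1 to 2 years.

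**True risk.** S(t) = exp(−0.02t), so S(1) to S(5) = 0.9802, 0.9608, 0.9418, 0.9231, 0.9048. The 5-year risk is 1 − 0.9048 = 9.5%. Yearly failure probabilities are 0.01980, 0.01941, 0.01903, 0.01865 and 0.01828.

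**Crude proportion over all implanted men** = Σ rᵢ × [S(i−1) − S(i)].

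- A: 0.01980 + 0.9×0.01941 + 0.8×0.01903 + 0.7×0.01865 + 0.6×0.01828 = 0.0765, or 7.7%.
- B: 0.01980 + 0.6×0.01941 + 0.45×0.01903 + 0.35×0.01865 + 0.25×0.01828 = 0.0511, or 5.1%.

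**Crude proportion over men with an event or a 5-year contact** = C / [C + r₅ × S(5)], with C the value above.

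- A: 0.0765 / (0.0765 + 0.6×0.9048) = 12.4%.
- B: 0.0511 / (0.0511 + 0.25×0.9048) = 18.4%.

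**Men followed through year 5 only.** The target is 9.5%, but only 60% or 25% of men are used. Per 1,000 implanted, SE = √(0.0952×0.9048/600) = 1.2 points or √(0.0952×0.9048/250) = 1.9 points.

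**Kaplan-Meier with event dates.** The target is 9.5%. By Greenwood's formula in continuous form, Var = S(5)² × G / n, where G = Σ [1/S(i) − 1/S(i−1)] / rᵢ. G = 0.1365 (A) or 0.2501 (B). Per 1,000 implanted, SE = √(0.8187×0.1365/1000) = 1.1 points or √(0.8187×0.2501/1000) = 1.4 points.

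**If loss is related to failure.** Let men lost before year 5 fail at k times the rate of the others, k = 0.5 to 2, with the overall risk held at 9.5%. The Kaplan-Meier limit is 1 − exp(−∫ mean hazard among men still followed). It runs from 8.4% to 10.5% (A) and 7.8% to 12.0% (B). The all-men crude proportion runs from 6.9% to 8.3% (A) and 4.5% to 5.9% (B). Kaplan-Meier is biased too, but less.

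**By device type.** Men at risk at year 5 = n × r₅ × 0.9048, from one year of enrolment under B to two years under A:

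| Device | At risk at year 5 | SE (points) |
|---|---|---|
| AMS 700 (n = 500 to 1,000) | 113 to 543 | 2.0 to 1.1 |
| Ambicor (n = 15 to 30) | 3 to 16 | 11.7 to 6.1 |
| Spectra (n = 20 to 40) | 5 to 22 | 10.1 to 5.3 |

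The SEs use the formula above and are only rough for the two small groups.

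**The case against.** The strongest reply is that time-to-event analysis is already planned. The synopsis commits to Kaplan-Meier over time, and mechanical malfunction is an example of a complication, so malfunctions may well be in that curve. On this view the gap is one undefined term and a mismatch of horizons, in an observational registry with no hypothesis or precision target. Much of that stands. A reader might infer that the plan rejects survival methods for durability or promises a crude 5-year proportion; the documents say neither. The 7.7% and 5.1% figures show what the committed summary would do if carried to several years, not an analysis that the plan specifies. What remains is that no reader can tell whether malfunctions and revisions are in the curve, or how far it runs.

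A second tempting inference is that the registry holds no event dates, so that even the 1-year curve is biased. The lists of event data in the synopsis and section 7.4.1 name complication, treatment, location and resolution, and no date. But section 7.4.1 introduces its list with "The information recorded will include the following", which need not be exhaustive, and the form is not shown. A planned Kaplan-Meier analysis presupposes event times, and the procedure date is collected. Section 7.4.2 keeps certain complaint details out of the registry database, but it is ambiguous on whether that removes an onset date. A dating bias is therefore not shown; the date is a point to confirm.

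A third objection is that late device-type curves for Ambicor and Spectra would be nearly uninformative. That is right, and the fix allows for it.

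**Conclusion.** The concern holds as a gap in the committed analysis. A main objective has no fixed estimand, event definition or time horizon, and the one summary clearly committed for complications in general is unsuited to unequal follow-up. Under the assumed rates, the same experience (true 5-year risk 9.5%) reads 7.7% or 5.1% over all implanted men, and 12.4% or 18.4% over men with an event or a 5-year contact.

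The size rests on the assumed 2% yearly hazard, complete follow-up through year 1 and the two retention patterns; none comes from the documents. With complete 5-year follow-up the crude proportion would be correct. The direction rests only on follow-up being unequal, which the design makes likely. Kaplan-Meier is unbiased only if loss to follow-up is unrelated to failure. This should be fixed before data lock; it does not undermine the registry.

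**What to change.** 1. In section 8.2, commit to time from procedure to first device malfunction and, separately, to first device- or procedure-related revision or explant, with mechanical and infection causes shown apart. Report at 1, 2, 3, 4 and 5 years as follow-up allows, overall and by device type. Use Kaplan-Meier censored at last contact, with numbers at risk and confidence intervals. Add cumulative incidence with death (and, for malfunction, removal for another cause) as a competing event. Keep the planned counts and proportions, with their denominator stated. Before data lock, set a minimum number at risk below which a device-type estimate is not quoted; this matters most for Ambicor and Spectra.
2. Reconcile the time horizon in the synopsis and section 8.2. List before data lock which events are *major*, and say whether malfunctions and revisions are among them.
3. Confirm that the event form captures onset date and the date of any revision or explant. If not, make them required fields. Where onset is unknown, use the interval between contacts.

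**Cost.** A few lines in section 8.2, a little more analysis work, and possibly two date fields with back-filling at up to 16 sites. Section 2.4 says lot numbers are not tracked, so recovering dates from complaint files may be hard. No extra patients or visits. Recalled dates will be imprecise, late risk sets sparse, and the assumption about loss to follow-up remains and should be stated with the results.

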### 7.4.3 SAFETY REPORTING

#### **Definitions and Classification**

Adverse event definitions are provided in Table 2. Administrative edits were made to combine definitions from ISO 14155-2011 and MEDDEV 2.7/3 (2015).

 Table 2: Safety Definitions

Table 2: Safety Definition	
Term	Definition
Adverse Event (AE) Ref: ISO 14155-2011	Any untoward medical occurrence, unintended disease or injury, or any untoward clinical signs (including an abnormal laboratory finding) in subjects, users or other persons, whether or not related to the investigational medical device.
Ref: MEDDEV 2.7/3 (2015)	
Serious Adverse Device Effect (SADE)	Adverse event that: a. Led to death, b. Led to serious deterioration in the health of the
Ref: ISO 14155-2011	subject, that either resulted in as defined by either: 1.a life-threatening illness or injury, or
Ref: MEDDEV 2.7/3 (2015)	2.a permanent impairment of a body structure or a body function, or
	
 
3.in-patient or prolonged hospitalization, or
 
4.medical or surgical intervention to prevent life-threatening illness or injury or permanent impairment to a body structure or a body function,
 

	c. Led to fetal distress, distress death or a congenital abnormality or birth defect.
	NOTE: Planned hospitalization for a pre-existing condition, or a procedure required by the Clinical Investigational Plan, without serious deterioration in health, is not considered a serious adverse event.
Unanticipated Adverse Device Effect (UADE)	Any serious adverse effect on health or safety or any life- threatening problem or death caused by, or associated with, a device, if that effect, problem, or death was not previously
Ref: 21 CFR Part 812	identified in nature, severity, or degree of incidence in the investigational plan or application (including a supplementary plan or application), or any other
	unanticipated serious problem associated with a device that relates to the rights, safety, or welfare of subjects.
Unanticipated Serious Adverse Device Effect (USADE)	Serious adverse device effect which by its nature, incidence, severity, or outcome has not been identified in the current version of the risk analysis report.
Ref: ISO 14155-2011	NOTE 1 : Anticipated serious adverse device effect (ASADE)
Ref: MEDDEV 2.7/3 (2015)	is an effect which by its nature, incidence, severity or outcome has been identified in the risk analysis report.

Table 2. Galety Deminitions		
Term	Definition	

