# 9 PROTOCOL DEVIATIONS

All attempts should be made not to deviate from the clinical protocol. If, however, a Protocol Deviation occurs a Protocol Deviation data form should be recorded for each study protocol deviation (e.g., failure to obtain written informed consent if required, enrolling a patient who does not meet inclusion criteria, not obtaining minimum required follow-up data). This form will include a description of the deviation, reason for deviation, and corrective and/or preventative action, if necessary. The Principal Physician is responsible for reporting protocol deviations in compliance with their IRB/EC regulations. BSC will determine and document whether the data obtained from patient(s) with one or more protocol deviations are sufficient to be included in the study outcomes analyses prior to locking the data for the analyses.

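### Does the 1-year Kaplan-Meier rate of major complications need a written definition, event date and censoring rule before it can be trusted?

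*Combined protocol and SAP*

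**What the plan says.** The synopsis announces that "Kaplan-Meier method will be used to estimate the event rate over time by device type for major complications". Section 8.2 narrows this to one time point: "Kaplan-Meier method will be used to estimate the major complication event rate at 1 year postoperative follow up by device type", and also for all recipients together. Neither place says which complications are major.

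Three other places could be read as supplying the meaning:

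- **Section 7.4.3, Table 2**, defines a serious adverse device effect, beginning "Adverse event that: a. Led to death, b. Led to serious deterioration in the health of the" subject, and goes on to hospitalization and to intervention to prevent permanent impairment.
- **Section 7.4.1** lists the reports on which the sponsor seeks more detail from the physician. These are serious effects, deficiencies that might have led to one, and an event that "or is severe and may pose unreasonable risk, or potential for death, or serious injury to the patient".
- **Section 8.2, Endpoint**, lists categories including "Revision procedures related to the device or implantation procedure" and "Deaths (related to the device or implantation procedure").

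On who is analysed, section 8.2 says "All enrolled patients that received a BSC penile prosthesis with data available will be included". Section 9 gives "not obtaining minimum required follow-up data" as an example of a deviation and has the sponsor decide and document, before data lock, whether data from men with deviations can be used.

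**The concern.** A Kaplan-Meier estimate needs an event, a time origin, an event time and a censoring rule. Section 8.2 leaves the first and the last two unstated. This is the only time-to-event method in section 8, and the only planned safety estimate beyond counts and proportions.

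The candidate definitions do not coincide. An infection treated as an inpatient without revision is serious under Table 2 but is not a revision. A same-day revision for mechanical failure is a revision, but it is serious only if read as preventing permanent impairment. The event items listed in section 7.4.1 are complication, treatment, location and resolution, with no date among them. Section 7.4.2 mentions an event start date only for the complaint unit, whose extra details stay outside the registry database. Section 9 could also be read as allowing men who miss the 1-year contact to be left out.

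Section 8 allows analyses from about 500 men and further ones as warranted, and section 16 says safety data may go to regulators. If the definition were chosen after the events were seen, rates in successive reports might not be comparable.

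**Working it through.** The documents state no complication rate, event count or power, so there is no figure of the plan's own to reproduce. The check has two parts.

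**1. The text, item by item**

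- *Relation to the device.* Table 2 starts from any adverse event, but section 8.2 opens by limiting the safety assessment to device- or surgery-related events, and its endpoint list limits deaths in the same way. Unrelated events do not enter.
- *Competing thresholds.* Section 7.4.1 describes when the sponsor asks for more information, and section 8.2 lists categories without a severity cut. Only Table 2 defines severity. The real ambiguity is whether *major* means serious, revised, or either.
- *Time origin.* A rate at 1 year after operation, with the procedure date a required item (section 7), points to implantation as time zero.
- *Event date.* The event form is not in the documents and the list in section 7.4.1 need not be complete. The documents do not show that onset dates are missing.
- *Risk set.* Section 8.2 gives the default set and section 9 a documented check before lock. Section 9 does not say that men without a 1-year contact are dropped. The two can be read together.

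**2. Sizes**

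*From the plan's counts (section 8.1, one to two years of enrolment, complete follow-up assumed).* Shift per event = 100/n points.

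| Device | n | Shift per event |
|---|---|---|
| Ambicor | 15 to 30 | 6.7 to 3.3 |
| Spectra | 20 to 40 | 5.0 to 2.5 |
| AMS 700 | 500 to 1000 | 0.2 to 0.1 |

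The exact 95% interval is 0.2% to 31.9% for 1/15 and 0.1% to 24.9% for 1/20. In these groups sampling error swamps the choice of definition.

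*Definition (all inputs assumed).* Let q = 0.10 of men have a related complication, r = 0.3 to 0.7 of those be revised, s1 = 0.3 to 0.6 of revised cases be serious and s0 = 0.1 to 0.3 of unrevised cases be serious.

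- Serious: q[r·s1 + (1−r)·s0] = 0.10(0.09 + 0.07) = 1.6% to 0.10(0.42 + 0.09) = 5.1%.
- Revision: q·r = 3.0% to 7.0%.
- Either: q[r + (1−r)·s0] = 0.10(0.30 + 0.07) = 3.7% to 0.10(0.70 + 0.09) = 7.9%.
- Either minus serious: q·r(1−s1) = 0.10·0.3·0.4 = 1.2 to 0.10·0.7·0.7 = 4.9 points.
- For comparison, the 95% half-width at 5% and n = 500 is 1.96·√(0.05·0.95/500) = 1.9 points.

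*Dating and censoring (simulated, true 1-year risk 5%, onset exponential, contact uniform over months 8 to 16).* The window is the one section 8.3 gives for effectiveness.

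- Onset date with censoring at last contact gives 4.9%. With 40% missing the 1-year contact and censored at implantation, it gives 4.8%.
- Dating every event at the reporting contact gives 2.8% with no interim contacts. Adding 3- and 6-month contacts and varying attendance and timing gives anything from 3.1% to 6.0%.
- Treating the 40% without contact as event-free to month 12 gives 2.8%.

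The ordinary convention recovers the truth when contacts are missed at random. The poor results need a rule that the plan does not state.

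**The case for a change.** The strongest opposing case is that this document is both protocol and SAP, so a quantity it commits to should be computable from it. A few lines would fix the definition, at no cost in visits or patients. Under the assumed inputs the gap between definitions (1.2 to 4.9 points) can exceed the sampling error for AMS 700, so there the choice would show.

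Part of this stands: *major* is undefined, and any report of the rate must say what it counted. The rest is weaker. Counts and proportions by complication category are reported beside the rate, and the endpoint list names serious effects and revisions separately, so the components can be seen whichever composite is used. Aggregate data are released only with committee approval (section 10), and the multi-center analyses are overseen by the sponsor with participating physicians (section 18).

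A rule written in haste may also do harm. Section 16.1 requires serious effects to be reported within 10 working days of the physician learning of them, so some events arrive between or after contacts. Suppose such events count by onset date while event-free men are censored at the last contact where the safety question was asked. If 70% of events present within a month, reports are accepted to month 16 and 80% to 100% of men are reached at 1 year (all assumed), a true 5% is estimated as 5.1% to 6.1%. Men with and without events have to be followed to the same cut-off, which is best judged with the data structure in hand.

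**Conclusion.** No change follows. This is missing detail in a descriptive registry estimate: no rule in the plan gives a wrong rate, and nothing in the plan is decided on the rate. A competent analyst would count the first related event per man, measure from implantation to onset or revision, censor at last follow-up in a way that treats men with and without events alike, and state which complications counted as major. Sections 8.2 and 9 do not conflict on who is included.

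The only size that rests on the plan's own counts is 100/n per event: up to 6.7 points for Ambicor, 5.0 for Spectra and 0.2 for AMS 700, assuming complete follow-up. It describes small device groups and would be the same under any definition. The definition and dating figures rest on assumed complication, revision, seriousness and attendance rates that the documents do not give. The conclusion would change only if the event form carried no usable onset or revision date, or if men without a 1-year contact were in fact excluded. The documents show neither.
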